# 11.0 Appendix

Grade	Symptomatology
0	Fully active, able to carry on all pre-disease performance without restriction
1	Restricted in physically strenuous activity but ambulatory and able to carry out work of a light or sedentary nature, eg, light house work, office work
2	Ambulatory and capable of all self-care but unable to carry out any work activities. Up and about more than 50% of waking hours
3	Capable of only limited self-care, confined to bed or chair more than 50% of waking hours
4	Completely disabled. Cannot carry on any self-care. Totally confined to bed or chair
5	Dead

### 11.1 Eastern Cooperative Oncology Group Performance Status Scoring

Source: (Oken, Creech et al. 1982)

### **11.2 Prohibited Concomitant Medications**

Prohibited medications and certain foods are not allowed in this study while participants are receiving study drug.

Strong CYP3A Inducers	CVP3A Substrates with a Narrow Therapeutic Window
Avasimibe, carbamazepine, phenytoin, rifampin, rifabutin, St. John's wort	Alfentanil, astemizole1, cyclosporine, dihydroergotamine, ergotamine, fentanyl, pimozide, quinidine, everolimus, sirolimus, tacrolimus, terfenadine 
	Sensitive P-gp Substrates with a Narrow Therapeutic Window
	Aliskiren, ambrisentan, colchicine, dabigatran etexilate, digoxin, everolimus, fexofenadine, imatinib, maraviroc, ranolazine, sirolimus talinolol, tolvaptan, topotecan

Note that this is not an exhaustive list. For an updated list, see the following **link:** http://www.fda.gov/Drugs/DevelopmentApprovalProcess/DevelopmentResources/DrugInteractionsL abeling/ucm080499.htm

CYP or P-gp substrates with a narrow therapeutic window refers to drugs whose exposure-response relationship indicates that small increases in their exposure levels by the concomitant use of CYP inhibitors may lead to serious safety concerns (eg, Torsades de Pointes).  Withdrawn from the US market because of safety reasons.

# **11.3 New York Heart Association Classification**

Class	Symptomatology
	No limitation of physical activity. Ordinary physical activity does not cause undue fatigue, palpitation, dyspnea, or anginal pain.
11	Slight limitation of physical activity. Comfortable at rest, but ordinary physical activity
	results in fatigue, palpitation, dyspnea, or anginal pain.
III	Marked limitation of physical activity. Comfortable at rest, but less than ordinary activity results in fatigue, palpitation, dyspnea, or anginal pain.
IV	Unable to carry on any physical activity without discomfort. Symptoms at rest. If any physical activity is undertaken, discomfort is increased.

Source: The Criteria Committee of the New York Heart Association. Nomenclature and Criteria for Diagnosis of Diseases of the Heart and Great Vessels. 9th ed. Boston, Mass: Little, Brown & Co; 1994:253-256.

# 11.4 Fridericia's Formula

QTcF=QT/RR^113

### 11.5 Medications Known to Prolong the QT Interval

amiodarone	citalopram	Escitalopram	methadone	sevoflurane
astemizole	clarithromycin	Flecainide	moxifloxacin	sotalol
azithromycin	disopyramide	Halofantrine	pentamidine	sparfloxacin
bepridil	dofetilide	Haloperidol	pimozide	terfenadine
chloroquine	domperidone	lbutilide	probucol	thioridazine
chlorpromazine	droperidol	Levomethadyl	procainamide	
cisapride	erythromycin	Mesoridazine	quinidine	

Please note that this is not an exhaustive list. For an updated list, see the following link: http://www.qtdrugs.org/medical-pros/drug-lists/drug-lists.htm

# ${\bf 11.6\,Representative\,Examples\,of\,Low-Fat\,and\,High-Fat,\,High-CalorieMeals}$

Low-fat breakfast:

A} 2 slices of white bread toast, 1 tablespoon light fat margarine, 1 tablespoon of jelly, and 8 ounces of skim milk (319 calories and 8.2 grams of fat}.

B) 1 cup of cereal, 1 slice of toast with jam, 8 ounces of skim milk, and 1 cup of decaffeinated coffee or tea (520 calories and 2 grams of fat).

**A** high-fat breakfast consists of the following and may be adapted to the local regional preference: 2 eggs fried in butter, 2 strips of bacon, 2 slices of white bread with butter, 1 croissant with 1 slice of cheese, and 8 ounces of whole milk. This representative high-fat breakfast contains approximately 1000 calories and 58 grams of fat.

# 11.7 National Cancer Institute Common Terminology Criteria for Adverse Events

The NCI CTCAE, version 5.0, can be accessed using the following link:

http://evs.nci.nih.gov/ftpl/CTCAE/CTCAE\_4.03\_2010-06-14\_QuickReference\_8.Sx11.pdf

### 11.8 RECIST vI.1

Tumor lesions are to be categorized as measurable versus non-measurable and target versus non-target based on RECIST vI.1 (Eisenhauer, Therasse et al. 2009).

### Measurable Lesions:

*Tumor lesions:* Must be accurately measured in at least 1 dimension (longest diameter in the plane of measurement is to be recorded) with a minimum size of:

10 mm by CT scan (CT scan slice thickness no greater than 5 mm).

10 mm caliper measurement by clinical exam (lesions which cannot be accurately measured with calipers should be recorded as non-measurable).

20 mm by chest X-ray.

*Malignant lymph nodes:* To be considered pathologically enlarged and measurable, a lymph node must be 15mm on the short axis when assessed by CT scan.

#### Non-measurable Lesions:

All other lesions, including small lesions (longest diameter <10 mm or pathological lymph nodes with 10 to <15 mm short axis) as well as truly non-measurable lesions, including leptomeningeal disease, ascites, pleural or pericardia! effusion, inflammatory breast disease, lymphangitic involvement of skin or lung, abdominal masses/abdominal organomegaly identified by physical exam that is not measurable by reproducible imaging techniques.

# Target Lesions:

When more than 1 measurable lesion is present at baseline all lesions up to a maximum of 5 total (and a maximum of 2 lesions per organ) representative of all involved organs should be identified as target lesions and measured at baseline.

Target lesions should be selected on the basis of their size (lesions with the longest diameter), be representative of all involved organs, but in addition should be those that lend themselves to reproducible repeated measurements.

Pathological lymph nodes that are defined as measurable and identified as target lesions must have a short axis of 15 mm by CT scan. Only the short axis of these nodes contributes to the baseline sum.

A sum of the diameters (longest for non-nodal lesions, short axis for nodal lesions) for all target lesions will be calculated and reported as the baseline sum diameters. The baseline sum diameters will be used as reference to further characterize any objective tumor regression in the measurable dimension of the disease.

### Non-target Lesions:

All other lesions (or sites of disease) including pathological lymph nodes should be identified as nontarget lesions and should also be recorded at baseline. Measurements are not required and these lesions should be followed as 'present', 'absent' or 'unequivocal progression.'

The following criteria outlined in Table 6 will be used to assess response to treatment.

	Response Criteria			
Category	Target Lesions	Non-Target Lesions/Tumor Markers		
Complete Response (CR)	Disappearance of all target lesions. Any pathological lymph nodes (whether target or non-target) must have reduction in short axis to <10 mm	Disappearance of all non-target lesions, and normalization of tumor marker level All lymph nodes must be non- pathological in size (<10 mm short axis).		
Partial Response (PR)	A 30% decrease in the sum of the diameter of target lesions, taking as reference the baseline sum diameter	N/A		
Stable Disease (SD)/ Incomplete Response	Neither sufficient shrinkage to qualify for partial response nor sufficient increase to qualify for progressive disease, taking as reference the smallest sum diameter since the treatment started	Persistence of 1 or more non-target lesion(s) and/or Maintenance of tumor marker levels above the normal limits		

Table 6:	Disease Response Criteria for Target and Non-target Lesions
----------	---

Progressive Disease	A 20% increase in the sum of the	Appearance of 1 or more new
	diameter of target lesions, taking as	lesions, and/or
	reference the smallest sum diameter recorded since the treatment started. In addition to the relative increase of 20%, the sum must also demonstrate an absolute increase of at least 5 mm, or The appearance of 1 or more new lesions	Unequivocal progression of existing non-target lesions

Target Lesions	Non-Target Lesions	New Lesions	Overall Response
CR	CR	No	CR
CR	Incomplete response/SD	No	PR
PR	Incomplete response/Non- Progressive disease	No	PR
SD	Incomplete response/Non- Progressive disease	No	SD
Progressive disease	Any	Yes or no	Progressive disease
Any	Progressive disease	Yes or no	Progressive disease
Any	Any	Yes	Progressive disease

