#### 1.4.3.1 Study AG120-C-002

Study AG120-C-002 is evaluating the safety, PK, PD biomarker patterns, and clinical activity of ivosidenib in participants with advanced solid tumors, including cholangiocarcinoma, with an IDHI

mutation. The primary objectives of the study are to assess the safety and tolerability of treatment with ivosidenib administered daily as a single agent dosed orally in participants with advanced solid tumors, including glioma, and to determine the maximum tolerated dose(s) (MTD[s]) and/or the recommended Phase 2 dose(s) of ivosidenib in this population. The initial dosing regimen was 100 mg BID and doses up to 1200 mg once daily (QD) were assessed in a 3+3 dose escalation design; based on the favorable PK profile showing a long elimination half-life ( $t^{1/2}$ ), BID dosing was discontinued after the first cohort and a QD dosing regimen was implemented. The study is divided into a dose escalation phase, followed by an expansion phase to allow for a more robust evaluation of the safety profile and preliminary assessment of clinical activity. This study is currently ongoing.

Efficacy data for Study AG120-C-002 were analyzed separately based on the underlying disease and specific response criteria, including Response Evaluation Criteria in Solid Tumors (RECIST), Response Assessment in Neuro-Oncology (RANO), Response Assessment in Neuro-Oncology for low grade glioma (RANO-LGG): cholangiocarcinoma, chondrosarcoma, or glioma. As of March 10, 2017, 73 participants with cholangiocarcinoma received ivosidenib in the dose escalation and expansion cohorts, with 62 participants receiving ivosidenib at 500 mg QD. Overall, 5% (n=4) experienced a confirmed partial response and 56% (n=41) experienced stable disease.

The 6-month PFS rate was 38.5% and the 12-month PFS rate was 21% (Lowery, Abou-Alfa et al. 2017). As of September 23, 2016, 21 participants with chondrosarcoma had been treated with ivosidenib and 20 were efficacy-evaluable. Eleven (55%) participants experienced stable disease as their best overall response; the remaining participants experienced disease progression (30%) or were not assessed (15%). The 3-month PFS rate was 58% with a median ivosidenib treatment duration of 2.6 months (range, 0 to 24 months) (Tap, et al. 2016).

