### 8.2 Statistical Analysis Plan

# 8.2.1 Primary Objective: Efficacy

Given that the response rate would be expected to be< 10% and PFS < 3.5 months in this patient population of IDHI mutant advanced solid tumors or gliomas, we will consider a participant to have had a positive outcome if they have a positive PFS6 (PFS6 is scored as either No or Yes) *and* they have had at least a partial response (evaluated by RANO in glioma patients and RECIST in patients with solid tumors) at the 12 week scan.

An Optimal Simon two-stage design is employed, where a probability of positive outcome less than 0.1 would not be promising and a probability of positive outcome 0.3 would warrant further interest. In the first stage, 18 participants will be accrued. If three or more participants have positive outcomes, 17 more participants will be accrued. If 7 or more out of the 35 participants have positive outcomes, the null hypothesis p<0.1 will be rejected at a=0.05. This design has 90% power if p > 0.3.

For all tumor types, six-month progression-free survival (PFS6) is defined as survival to six months after the initiation of treatment without objective tumor progression

The probability of positive outcome and 95% confidence interval will be estimated using the method of Koyama and Chen (Koyama and Chen 2008).

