# Table 8: Assessment of Best Overall Response

Best Overall Response	Criteria
Complete Response (CR)	CR observed in consecutive assessments 2'. 4 weeks apart per RANO
Partial Response (PR)	PR observed in consecutive assessments 2'. 4 weeks apart per RA $0$
	SD observed and does uot qualify for CR or PR
Stable Disease (SD/	or Suspected PD followed with histologic results not confinning PD, and n CR, PR or SD observed
Not valuable ( )	Insufficient data to detennine disease progression or response
Progressive Disease (PD)	No CR, PR, or SD prior to PD

a To qualify for SD there must be a minimum on-treatment period of 10 weeks.

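### The pooled primary count requires a glioma partial response to hold for at least 4 weeks, but states no confirmation for a solid-tumor one

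*Combined protocol and SAP*

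**What the plan says.** **Success definition (Section 8.2.1).** A participant is a success if PFS6 is Yes and, in addition, "they have had at least a partial response (evaluated by RANO in glioma patients and RECIST in patients with solid tumors"). This is read on a scan that the section places at 12 weeks. No confirmation rule is added. Section 2.2.1 sets the response reading at 8 weeks, and Section 3.1 schedules scans every 8 weeks (±7 days).

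**Solid tumors (Section 11.8, Tables 6 and 7).** PR is "A 30% decrease in the sum of the diameter of target lesions, taking as reference the baseline sum diameter". No repeat scan or minimum duration is stated. Progression is a 20% rise, and at least 5 mm, over the smallest sum recorded since treatment started.

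**Glioma (Section 11.9).** The RANO table requires the 50% decrease to be sustained for at least 4 weeks. Table 8 gives the best-response rule as "PR observed in consecutive assessments" at least 4 weeks apart.

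**Decision rule (Section 8.2.1).** The two boundary rates are set by this statement: "a probability of positive outcome less than 0.1 would not be promising and a probability of positive outcome 0.3 would warrant further interest". Stage 1 enrolls 18, and its go rule reads: "If three or more participants have positive outcomes, 17 more participants will be accrued". The final test, on both stages together, reads: "If 7 or more out of the 35 participants have positive outcomes, the null hypothesis p<0.1 will be rejected at a=0.05". The claimed power is given last: "This design has 90% power if p > 0.3".

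**Background (Section 1.4.3.1).** In cholangiocarcinoma on ivosidenib alone, "5% (n=4) experienced a confirmed partial response", 56% had stable disease, and the 6-month PFS rate was 38.5%.

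**The concern.** One binary outcome is scored by two standards, and the looser one applies to only one tumor group. Suppose a solid tumor reads −31% at the qualifying scan and −20% at the next, with no progression by six months. It counts as a success. A glioma that crosses its own threshold once and falls short at the next scan does not.

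The trial is single-arm and is decided on whether the count reaches 7 of 35, so no control group absorbs chance responses. The meaning of the pooled rate also depends on the tumor mix enrolled.

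**Working it through.** **1. The plan's own figures.** Inputs from Section 8.2.1: 18 in stage 1, continue at 3 or more; 35 in total, reject at 7 or more.

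P(reject | p) = Σ (x = 3 to 18) Bin(x; 18, p) × P(Bin(17, p) ≥ 7 − x)

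- p = 0.10: 0.0474
- p = 0.30: 0.9016

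The stated 5% and 90% reproduce. Solving P(reject) = 0.05 gives p = 0.1012, so a rise of about 0.001 in the counted null rate uses up the slack.

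**2. The two standards side by side.**
- Solid tumor, baseline sum 100, readings 69 then 80. The rise from nadir is (80 − 69)/69 = 15.9%, below 20%, so there is no progression. With PFS6 = Yes this is a success.
- Glioma is measured on products of diameters, so take 48 then 55. The first is a 52% decrease. The rise is (55 − 48)/48 = 14.6%, below the 25% progression threshold. The second reading is only a 45% decrease, so the PR is not sustained and this is a failure.

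**3. What the nadir rule removes.** After a reading of 69, any later sum of 1.2 × 69 = 82.8 or more (−17.2% or worse) is progression.

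Illustration, with values not in the documents: true change −20%, normal error with SD 8–10 points.
- One-scan false PR: Φ(−10/8) = 10.6% to Φ(−10/10) = 15.9%.
- Simulation with scans at weeks 8, 16 and 24, independent errors, and both the 20% and 5 mm conditions (baseline sum 100 mm): if the PR is read at week 8, 75–80% of these are later scored as progression. If it is read at week 16, 53–59% are.
- Surviving share, week 8: 10.6% × 0.25 = 2.7% to 15.9% × 0.20 = 3.2%. Among those still progression-free this becomes about 3.5–4.7%.
- If true changes are instead spread evenly from −25% to +10%, the week-8 figure among the progression-free is 1.3–1.7%.

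This supports a working range of f = 1.5–5%. The upper end is not a bound. For a week-16 reading with every participant truly at −20%, the surviving share before restricting to the progression-free is already 10.6% × 0.47 = 5.0% to 15.9% × 0.41 = 6.5%.

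**4. Effect on type I error.** Counted rate = p + s·q·f, where s is the solid-tumor share (assumed), q the proportion progression-free without a true PR, and f as above. With PFS6 of 38.5% and a true joint rate of 0.10, q is at most 0.385 − 0.10 = 0.285. The lower value 0.20 is an assumption.

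| s | q | f | counted rate | P(reject) |
|---|---|---|---|---|
| 1 | 0.20 | 0.015 | 0.1030 | 0.054 |
| 1 | 0.20 | 0.05 | 0.1100 | 0.072 |
| 1 | 0.285 | 0.05 | 0.1143 | 0.0845 |
| 0.5 | 0.20 | 0.015 | 0.1015 | 0.051 |
| 0.5 | 0.285 | 0.05 | 0.1071 | 0.064 |

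The largest row adds 35 × 0.285 × 0.05 = 0.5 expected successes.

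**5. If the true joint rate is 0.05.** Here q = 0.385 − 0.05 = 0.335. With f = 5%, P(reject) is 0.003–0.006 for s between 0.5 and 1. It exceeds 0.05 only at the extreme examined, f = 20% with every participant a solid-tumor patient (0.093).

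**6. Power cost of confirmation.** If confirmation removes 5% or 10% of true positives, p1 becomes 0.30 × 0.95 = 0.285 or 0.30 × 0.90 = 0.27. Power falls from 0.902 to 0.869 or 0.828.

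**The case against.** **The composite outcome already filters noise.** This stands in large part. A falsely low scan sets a falsely low nadir, so regression toward the true value is often scored as progression. The filter is incomplete, as the 69-then-80 case shows.

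**A larger inflation might be inferred.** Applying a raw false-PR rate of 5–10% to 20–30% of participants gives counted rates of 0.110–0.130 and type I error of 7.2–14.1%. The documents do not support that range. It ignores the nadir rule, its 30% exceeds the 28.5% that the cited PFS6 allows at a true rate of 0.10, and it treats every participant as a solid-tumor patient.

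**The true rate may lie well below 0.10.** The joint outcome cannot exceed the PR rate, which was 5% in cholangiocarcinoma, and in chondrosarcoma no best response above stable disease was reported. Rejection is then rare with or without confirmation. This limits the practical risk, but type I error is defined at the plan's own boundary of 0.10.

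**Non-comparability with history.** A reader might infer that the null rate is a confirmed rate. Section 8.2.1 ties 0.10 to an expected response rate under 10%, not to the 5% figure. The other cited rates (8%, under 5% and 0% in Section 1.2.1; 8% in the earlier cholangiocarcinoma cut) are not labelled confirmed. Only comparison with the 5% figure is affected.

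**RECIST 1.1 is adopted by reference.** The gap is an inference from silence in Tables 6 and 7 and Section 8.2.1. Whether the guideline supplies a rule for this setting cannot be settled from the documents, which is a reason to state one.

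**Conclusion.** The inconsistency is clear on the text: one pooled count, with a 4-week requirement for glioma PR and none stated for solid-tumor PR. Its numerical effect is modest. At a true joint rate of 0.10, type I error is roughly 5–8% against an exact 4.7%. That rests on assumed values for the false-PR rate, measurement error, tumor mix and exposed proportion, and on single-agent cholangiocarcinoma PFS6 carrying over to this trial. With half the participants having solid tumors it is about 5–6%. Near a true rate of 0.05 it stays below 5% in most scenarios.

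The size also depends on which scan qualifies, since an earlier reading leaves more later scans at which a false PR can be overturned. The plan does not settle that. This is a worthwhile, inexpensive correction, not a failure of the design: the 18/35 structure and its cut-offs can stay.

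**What to change.** In Sections 8.2.1 and 11.8, state one rule for both groups: a CR or PR counts toward the positive outcome only if it is still present at an assessment at least 4 weeks later, and the next scheduled 8-weekly scan can serve.

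In the same edit, name the qualifying scan by reconciling week 8 (Section 2.2.1), week 12 (Section 8.2.1) and the 8-weekly schedule (Section 3.1), which has no week-12 scan. A week-8 response would be confirmed at week 16, and a week-16 response at week 24. Both fall before the six-month reading. Report unconfirmed response as a supportive figure.

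**Cost.** Wording only, with no added scan or delay. The observed rate may be lower. If 0.30 was meant for unconfirmed response, restate power: about 87% if confirmation removes 5% of true positives, about 83% if it removes 10%. Both scans share the same baseline measurement, so confirmation reduces false responses without eliminating them. The rule should be fixed before outcomes are known, because it could decide whether the count is 6 or 7.

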# Table 7: Overall Disease Response Criteria

Abbreviations: CR= complete response; PR= partial response; SD= stable disease.

# 11.9 RANO Criteria Table 11.9.1: RANO Criteria for Response Assessment Incorporating MRI and Clinical Factors

Response	Criteriaa		
Complete response	Requires all of the following: complete disappearance of all enhancing measurable and nonmeasurable disease sustained for at least 4 weeks; no new lesions; stable or improved nonenhancing (Tl/FLAIR) lesions; subjects must be off corticosteroids (or on physiologic replacement doses only) and stable or improved clinically. ote: subjects with nonmeasurable disease only cannot have a complete response; the best response possible is stable disease.		
Partial response	Requires all of the following: 2:'. 50% decrease compared with baseline in the sum of products of perpendicular diameters of all measurable enhancing lesions sustained for at least 4 weeks; no progression of nonmeasurable dis ase no new lesions; stable or .improved nonenhancing (T2/FLAIR) lesions on same or lower dose of corticosteroids compared with baseline scan; the corticosteroid dose at the time of the scan evaluation should be no greater than the dose at time of baseline scan; and stable or improved clinically. Note: Subjects with nonmeasurable d.isease only cannot have a partial response; the best response possible is stable disease.		
Stable disease	Requir s a!] of the following: does not qualify for complete response, partial response, or progression; stab.le nonenhancing (T2/FLAIR) lesions on same or lower dose of corticosteroids compared with baseline scan. In the event that the corticosteroid dose was increased for new symptoms and signs without confirmation of disease progression on neuroi.maging, aud subsequent follow-up imaging shows that thi increase in corticosteroids was required because of disease progression, the last scan considered to		

	show stable disease will be the scan obtained when the corticosteroid dose was equivalent to the baseline dose.
Progression	Defined by any of the following: ;;,: 25% increase in sum of the products of perµ ndicular diameters of enhancing lesions compared with the smallest tumor measurement obtained either at baseline (if no decrease) or best response, on stable or increasing doses of corticosteroids•; significant increase in T2/FLAIR nonenhancing lesions on stable or increasing doses of corticosteroids compared with baseline scan or best response after initiation oftberapy' not cause by comorbid events (eg, radiation therapy, demyelination, ischernic injury, infection, seizures, post-operative changes, or other treatment effects); any new lesion; clear clinical deterioration not attributable to other causes apart from the tumor eg, seizures, medication adverse effects, complications of therapy, cerebrovascular events, infection, and so on) or changes in corticosteroid dose; failure to return for evaluation as a result of death or deteriorating condition; or clear progression of nonmeasurable disease.

NOTE: Radiologic interpretation guidelines, definitions and rumor measurement instructions will be provided separately in a separate imaging manual. All measurable and nonmeasurable lesions must be assessed using the same techniques as at baseline.

Abbreviations: MRI, magnetic resonance imaging. FLAIR, fluid-attenuated inversion r covery

\* Stable doses of corticosteroids include subjects not 011 corticosteroids

a From: Wen PY, Macdonald DR, Reardon DA, Cloughesy TF, Sorenson AG, Galanis E, et al. Updated Response Assessment Criteria for High-Grade Gbomas: Response Assessment in euro-Oncology Working Group; J Clin Oncol. 2010 Apr IO; 28(11):1963-72.

